5.0 CLINICAL TRIAL INVESTIGATIONAL PRODUCT INFORMATION

5.1 INVESTIGATIONAL PRODUCT (IP) AND STUDY DEVICE

5.1.1 **INO-4800 AND PLACEBO**

Investigational product is defined as a pharmaceutical form of an active ingredient or placebo being tested or used as a reference in the study, whether blinded or unblinded.

INO-4800 is the active investigational product to be used in this study. The INO-4800 drug product contains 10 mg/mL of the DNA plasmid pGX9501 in 1X SSC buffer (150 mM sodium chloride and 15 mM sodium citrate). pGX9501 is a DNA plasmid expressing a synthetic consensus (SynCon[®]) sequence of the SARS-CoV-2 full length Spike glycoprotein.

Phase 2 segment:

Active Investigational Product (INO-4800): A volume of 0.4 mL will be filled into 2-mL glass vials that are fitted with rubber stoppers and sealed aluminum caps.

Placebo: Sterile saline sodium citrate (SSC) buffer, which contains sterile 150 mM sodium chloride and 15 mM sodium citrate in 10-mL glass vials, stoppered, and sealed with aluminum caps.

Phase 3 segment:

INO-4800	COVID19-311
Inovio Pharmaceuticals, Inc.	Clinical Protocol

Active Investigational Product (INO-4800): A volume of 0.4 mL, 0.8 mL, or 1.5 mL will be filled into 2R glass vials that are fitted with rubber stoppers and sealed aluminum caps.

Placebo: Sterile saline sodium citrate (SSC) buffer, which contains sterile 150 mM sodium chloride and 15 mM sodium citrate at a volume of 0.8 mL or 1.5 mL in 2R glass vials, stoppered, and sealed with aluminum caps. Placebo may also be referred to as Placebo for INO-4800 or Sterile SSC Buffer.

5.1.2 **CELLECTRA® 2000**

Electroporation is a procedure used to enhance cellular DNA uptake within host cells following DNA vaccine ID delivery. This study will use the CELLECTRA[®] 2000, a portable, battery-powered medical device designed to generate a controlled, electric field that temporarily and reversibly increases cellular membrane permeability without clinically damaging the tissue. During the period of increased permeability, injected plasmid DNA can be introduced into the cells.

As mentioned above, the CELLECTRA[®] 2000 device is intended to enhance the uptake and expression of DNA plasmid-based biologics in order to enhance vaccine efficacy. The DNA plasmid is delivered separately via needle and syringe ID injection immediately prior to the electroporation. The electroporation is accomplished through a sterile, disposable needle Array attached to an Applicator delivering controlled electrical pulses as follows:

- An EP administration consists of four pulses.
- An array of three stainless steel electrode needles is used to deliver the electrical pulses into the tissue. The Array needle length that penetrates into the skin and tissue is approximately 3.2 mm. To date, we have not had any safety concerns associated with the depth of the array electrode needles. Within the Array needle depth of 3.2 mm, there are no major blood vessels (arteries, veins) or nerve structures at the authorized sites of administration overlying the deltoid or the anterolateral quadricep muscle. There are superficial capillaries and minor nerves innervating the skin, including subcutaneous tissues that may be disrupted by needle insertion, but are extremely unlikely to result in serious injury; intradermal injection followed by EP of these structures poses no significant risk to the subject except for possibly injection site reactions.
- The CELLECTRA[®] 2000 generates four 52ms ±1ms electrical current controlled DC pulses. The nominal current is set to 0.2A ±10% by modulating voltage, or capped at 200V ±5%, determined by patient tissue impedance.
- The total energy delivered by the device is determined by the combination of four device parameters: Pulse Current, Pulse Voltage, Number of Pulses, and Pulse Width. The parameters are pre-set by Inovio to be a pulse current of 0.2A, a pulse voltage of 200V, and 4 pulses at 52ms pulse width. The parameters are verified prior to shipment and cannot be changed by the user.
- In eight clinical trials administering ID injection followed by EP using the CELLECTRA® 2000, total energy delivered ranged from 0.9J to 7.8J, which have been generally safe and well-tolerated. In addition, Inovio has calculated the total maximum energy delivered ID as 8.32J for normal use conditions. Higher energy pulses ranging from 10.7J to 11.7J were evaluated in a guinea pig model which induced erythema localized to the electrode insertion site. Taken together, these nonclinical data and Inovio's clinical experience provide evidence that the total energy delivered by the CELLECTRA® 2000 device will not result in unacceptable risks when delivered to patients. Further, a published study

INO-4800	COVID19-311
Inovio Pharmaceuticals, Inc.	Clinical Protocol

evaluated the Visual Analog Scale (VAS) pain scores of normal use conditions (0.2A), and found ID injection followed by EP using the CELLECTRA[®] 2000 device to be safe and well tolerated [65].

• The specified current is constantly maintained through voltage modulation using an analog feedback loop. Measurements of voltage and current are processed for error reporting and collected for data logging.

The CELLECTRA[®] 2000 device is comprised of three components: (1) A battery-powered Pulse Generator, (2) an ID Applicator that is connected to the pulse generator, and (3) a three-point sterile disposable ID Array of stainless steel needles. The Pulse Generator and ID Applicator are reusable components. These components should be cleaned and disinfected prior to each subject's use according to the Cleaning and Maintenance procedure in the User Manual. The Pulse Generator and ID Applicator have been validated for up to 30 cleaning and disinfection cycles based on a maximum of 30 subjects being treated in a day. Therefore, the Pulse Generator and ID Applicator's use should be limited to 30 subjects in a day. Any potential risk of damage to the device due to cleaning and disinfection for more than 30 cycles has not been validated. Always inspect the device before use according to the instructions in the Maintenance section of the User Manual.

5.2 **Dosing Regimens**

Phase 2 Segment

- Active Investigational Product: One or two 1.0mg ID injection(s) of INO-4800 (~0.1mL dose volume each) followed immediately by EP administered on Day 0 and Day 28 (±3 days)
- Placebo: One or two ID injection(s) of placebo (~0.1mL) followed immediately by EP administered on Day 0 and Day 28 (±3 days)

Phase 3 Segment

- Active Investigational Product: Two 1.0mg ID injections of INO-4800 (~0.1mL dose volume) followed immediately by EP administered in separate limbs on Day 0 and Day 28 (±3 days)
- Placebo: Two ID injections of placebo (~0.1mL) followed immediately by EP administered in separate limbs on Day 0 and Day 28 (±3 days)

5.2.1 BLINDING

This study is blinded. The Sponsor, subjects and clinical site staff, with the exception of the site's pharmacy personnel, will be blinded. There is no difference in appearance between INO-4800 and the placebo; however, they are distinguishable based on the vial size and/or labelling on the vials. In the Phase 2 segment, the vials will be of different sizes and have unblinded labelling. In the Phase 3 segment, the vials will be the same size but will have unblinded labelling. To maintain the blind, vials will only be handled by designated unblinded personnel (site pharmacist) at the site.

Under exceptional circumstances, the PI may desire to unblind a subject's dose assignment in case of an emergency or serious medical condition when knowledge of the study product or dose is deemed by the PI to be absolutely essential for proper clinical management of the subject. Under such emergency circumstances, the Sponsor urges the PI to first contact the Medical Monitor (MM) to review options before unblinding the subject's dose assignment. In case of non-emergency, PI must contact MM to discuss the options before unblinding the subject's dose assignment.

INO-4800	COVID19-311
Inovio Pharmaceuticals, Inc.	Clinical Protocol

It is not deemed appropriate to unblind a subject's treatment assignment for the purpose of assisting the subject in making a decision regarding receipt a different COVID-19 vaccine (emergency use or licensed vaccine). Subjects may be advised that without efficacy data, INO-4800 has not been proven to be more protective than placebo in the prevention of COVID-19 and SARS-CoV-2 infection. Therefore, unblinding will not provide any meaningful information to inform a decision of receiving a different COVID-19 vaccine.

The Sponsor's pharmacovigilance staff may unblind a subject's dose assignment for an SAE, unanticipated adverse device effect (UADE), or adverse event of special interest (AESI) when the event is assessed as related and unexpected. If expedited regulatory reporting is required for such an event, the report may be submitted to regulatory authorities with the subject's dose assignment, in accordance with local regulations.

The Phase 2 segment of the trial will be unblinded following subjects reaching the Week 30 visit.

5.3 **PACKAGING AND LABELING**

5.3.1 **INO-4800 OR PLACEBO**

Each vial of INO-4800 or placebo will be labeled consistent with the example product label provided in the IB.

5.3.2 **CELLECTRA® 2000**

Please see shipping box for shipping documents and contents.

The CELLECTRA® 2000 device and its components bear labels that identify the device name and place of business of the manufacturer. The CELLECTRA® 2000 User Manual describes all relevant contraindications, hazards, potential risks and adverse effects, interfering substances or devices, warnings, and precautions. Each Pulse Generator has a unique serial number, and each ID Applicator has a unique serial number. Each ID Array has a Lot Number and Expiration Date. Examples of device labels are provided in the IB.

The CELLECTRA[®] 2000 device, and its components, will be shipped directly from the manufacturer to the study site.

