Adverse Events ^h	Х	Х	Х	Х	Х	Х	Х	Х	Х	Х	Х	Х	Х
Cellular Samples ⁱ		Х						Х		Х	Х		Х
Humoral Samples ^j		Х						Х		Х	Х		Х
SARS-CoV-2 Serology ^k	Х												
SARS-CoV-2 RT-PCR (Saliva and Swabs)	XI	1			l							XI	XI
Distribute Diary		1	Х		l	Х							
Review/Collect Diary ^o	1			Х	Х		Х	Х					

INO-4800 Inovio Pharmaceuticals, Inc.

- a. Screening assessment occurs from -30 days to -1 day of Day 0.
- b. Full physical examination only at Screening and Day 393 (or EOS). Targeted physical exam at other indicated visits.
- c. Hemoglobin A1c collected at screening only. Chemistry includes Na, K, Cl, HCO₃, Ca, PO₄, glucose, BUN, Cr, alkaline phosphatase, AST, ALT, LDH, total bilirubin.
- d. Dipstick for glucose, protein, and hematuria. Microscopic examination should be performed if dipstick is abnormal.
- e. Serum pregnancy test at Screening. Urine pregnancy test at other visits.
- f. Intradermal injection(s) in skin preferably over deltoid muscle, or alternately over anterolateral quadriceps muscle, followed by EP at Day 0 and Day 28.
- g. Following administration of INO-4800 or placebo, EP data will be downloaded from the CELLECTRA® 2000 device and provided to Inovio.
- h. AEs to be collected from time of consent to Day 56; SAEs, MAAEs, and AESIs to be collected from time of consent to EOS.
- i. On Day 0, cellular sampling requires 64 mL of whole blood (8 Cell Preparation Tubes (CPT), each 8 mL of whole blood) prior to 1st dose. At all other time points, collect 32 mL of whole blood (4 CPT tubes, each 8 mL of whole blood).
- j. On Day 0, humoral sampling requires a total of 17 mL of whole blood (two 10-mL red top serum collection tubes, each 8.5 mL of whole blood, to produce eight serum aliquots of 1 mL each). At all other time points, collect 8.5 mL of whole blood in a single 10-mL red top serum collection tube to produce four serum aliquots of 1 mL each.
- k. SARS-CoV-2 antibody.
- I. Saliva specimen at Screening; Nasal swabs and saliva specimens at COVID-19 assessment and convalescent visits. Genotyping may also be performed on sample(s) collected at the COVID-19 assessment visit.
- m. Subjects will be evaluated during a "COVID-19 assessment visit" when acute COVID-19 is suspected. The assessment visit may be performed in the clinic, in the subject's vehicle or at the subject's home and should be completed within 3 days of symptom onset or within 3 days of a positive result of a SARS-CoV-2 test.

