6.1.2 CLINICAL TRIAL EVALUATIONS AND PROCEDURES

Once eligibility has been confirmed, the subject will be randomized to receive a treatment assignment (INO-4800 or placebo). Visit dates and windows must be calculated from Day 0, unless otherwise noted. All subjects will be followed until the Day 393 Visit. All subjects will be followed in accordance with assessments outlined below.

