6.1.2.4 Phone calls

Phase 2 segment: Day 56

Phase 3 segment: Days 56, 70, 84, 98, 112, 140, 154, 168, 182, 196, 238, 266, 322, 350, and 378

In the Phase 3 segment, phone calls to subjects have been spaced bi-weekly between study visits through Day 210, and approximately monthly between visits from Day 210 to Day 393.

Guidelines for information to be collected during the phone call can be found in the Phone Script. The following evaluations will be performed during the phone call:

- Collect all present and/or new or ongoing AEs (Section 6.4.4); only SAEs, AESIs and MAAEs will be reported after the Day 56 Visit;
- Ask about any symptoms of COVID-19 disease; Arrange on-site visit if any signs and symptoms of COVID-19 disease are present (Section 6.4.9);
- Record current concomitant medications/treatments (Section 6.4.6);

6.1.2.5 **Follow up clinic visits**

Phase 2 segment: Day 210 Phase 3 segment: Days 126, 210 and 294 Visits

Both Phase 2 and Phase 3 segments: The following evaluations will be performed at these visits:

- Collect all present and/or new or ongoing AEs (Section 6.4.4); SAEs, AESIs, and MAAEs will be reported after the Day 56 Visit.
- Document any present conditions and concomitant illnesses;
- Record current concomitant medications/treatments (Section 6.4.6);
- Ask about any symptoms of COVID-19 disease;
- Targeted physical examination (Section 6.4);
- Record vital signs (Section 6.4);
- Collect whole blood and serum for cellular and humoral immunology assessment (Phase 3 Day 201 visit only; Phase 3 cellular immunology collection at selected sites only) (Section 6.5);

Phase 3 segment:

- Collect serum for SARS-CoV-2 antibody testing (Section 6.4.8);
- Ensure subject has necessary supplies at home (e.g. thermometer).

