Actual or estimated start and stop dates must be provided. This information will be obtained from the subject and/or any available medical records. The indication for the medication, dose, and dose regimen will be documented.

Therapy considered necessary for the subject's welfare may be given at the discretion of the Investigator or medical provider. If the permissibility of a specific medication/treatment is in question, please contact the Medical Monitor.

The decision to administer a prohibited medication/treatment (Section 6.4.7) is made with the safety of the clinical trial subject as the primary consideration. When possible, the Sponsor should be notified before the prohibited medication/treatment is administered.

6.4.7 **RESTRICTIONS**

In the Phase 2 segment of the trial, subjects should refrain from becoming pregnant until 3 months following the last dose of investigational product by using appropriate

INO-4800	COVID19-311
Inovio Pharmaceuticals, Inc.	Clinical Protocol

contraceptive measures (see Section 4.1.1). In the Phase 3 segment of the trial, subjects should refrain from becoming pregnant until receipt of the last dose of investigation product by using appropriate contraceptive measures (See Section 4.1).

Subjects must not receive any non-study related vaccine (e.g., influenza vaccine) within 2 weeks prior to the first dose of IP, or within 2 weeks of (before or after) any subsequent dose of IP.

Subjects must not have fever (oral temperature \geq 38.0 degrees Celsius or 100.4° Fahrenheit) within 72 hours prior to each dosing.

Subjects should not receive hydroxychloroquine during the trial. In the Phase 3 segment, subjects should not receive any other drug/vaccine intended as COVID-19 prophylaxis during the trial.

For subjects in the Phase 2 segment of the trial, the receipt of any non-study prophylactic COVID-19 vaccine (authorized under emergency use or licensed) is no longer restricted, based upon increasing availability of EUA vaccine and completion of the Phase 2 data for purposes of Phase 3 dose selection.

If a subject informs the site of their intent to receive a non-study prophylactic COVID-19 vaccine (available either under emergency use or when licensed), the subject should be informed that the safety and effectiveness of receiving INO-4800 followed by receipt of another COVID-19 vaccine has not been studied.

Subjects should not participate in any other interventional trials for the duration of this trial.

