8.5.3 SAFETY ANALYSES

8.5.3.1 Adverse Events

All AEs including injection-site reactions will be summarized among the Safety Population by frequency per treatment arm. These frequencies will be presented overall and separately by dose, and will depict overall, by system organ class and by preferred term, the percentage of subjects affected. Additional frequencies will be presented with respect to maximum severity and to strongest relationship to Study Treatment. Multiple occurrences of the same AE will be counted only once following a worst-case approach with respect to severity and relationship to Study Treatment. All serious AEs will also be summarized as above.

The main summary of safety data will be based on events occurring within 30 days of any dose. For this summary, the frequency of preferred term events will be compared between study arms with risk differences and 95% confidence intervals, using the method of Miettinen and Nurminen. As this analysis will use many event categories, and produce many confidence intervals, caution should be exercised when interpreting these confidence intervals. Separate summaries will be based on events occurring within 7 days of any dose and regardless of when they occurred.

The analyses listed above will be performed according to the Phase of the trial. For the Phase 2 segment, the analyses listed above will also be performed according to prior receipt of any non-study prophylactic COVID-19 vaccine. For the Phase 3 segment, the analyses listed above will also be performed according to SARS-CoV-2 serostatus at baseline.

For AE data, partial start dates will be imputed to the date of treatment to conservatively report the event as treatment-emergent, whenever the portion of the date is consistent with that of the study treatment. Otherwise, it will be imputed to the earliest date consistent with the partial date. A completely missing onset date will be imputed as the day of treatment. Partial stop dates will be assumed to be the latest possible day consistent with the partial date. AE duration will be calculated as (Stop Date – Start Date) + 1.

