8.5.6 INTERIM ANALYSES

For safety issues, the DSMB could recommend stopping enrollment at any time; no formal interim analysis will be performed for this purpose. The two-sided type I error of 0.05 will not be adjusted for possible early stopping due to this aspect.

For the Phase 2 segment, group-level unblinded summaries of the immunogenicity and safety data will be produced once Week 6 visit immunology data and Week 8 visit safety data are complete for all subjects who have not discontinued, while maintaining subject-level blinding. Long-term follow-up data will continue to be collected for all subjects who have not discontinued with remaining visits through the final visit. These summaries will allow the Sponsor to have results for the purposes of dose selection for the Phase 3 portion. No subject-level immunogenicity data will not be available in the clinical trial database until all other clinical trial data are finalized at the end of the trial. No safety summary will be provided if the total number of subjects who experience the event of interest is greater than 0 and the count of the number of subjects with the event in a given treatment group relative to the

INO-4800	COVID19-311
Inovio Pharmaceuticals, Inc.	Clinical Protocol

total produces a percentage less than 3%, for a given summary. The group-level unblinded production of the summaries will not include anyone directly involved with the trial or any additional unblinded personnel; only the external Contract Research Organization (CRO), ICON, which will already be providing unblinded summaries for the Data Safety Monitoring Board, will be utilized. Thus, the trial will remain blinded to the Sponsor with respect to subject treatment assignment.

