8.5.9.3 Concomitant Medications

Concomitant medications are those used during the course of the trial (on or after Day 0). Partial stop dates of concomitant medications will be assumed to be the latest possible date consistent with the partial date; start dates will not be imputed. Data for all concomitant medications will be summarized with percentages by treatment arm, for the ITT and PP populations. These summaries will be performed according to Phase. For the Phase 3 segment, the analyses listed above will also be performed according to SARS-CoV-2 serostatus at baseline.

8.6 **SAMPLE SIZE/POWER**

Phase 3 segment: The trial is case-driven. A total of 17 observed severe cases among baseline SARS-CoV-2 seronegative and RT-PCR negative subjects will be required to provide 90% power to declare the vaccine efficacious (>30%), assuming a true efficacy of 90% and utilizing the methodology described in Section 8.5.1. A sample size of 10,002 baseline SARS-CoV-2 seronegative subjects is expected to be required to achieve this number of cases assuming an underlying attack rate of approximately 0.4%.

8.7 **RANDOMIZATION AND BLINDING**

Phase 2 Segment

Subjects will be randomized (3 INO-4800 1.0 mg, one injection: 3 INO-4800 2.0 mg, two injections:1 Placebo, one injection: 1 Placebo, two injections).

The study is blinded. It is double-blinded within dose group. Randomization and blinding will avoid bias in the assignment of subjects to treatment, increase the likelihood that known and unknown subject attributes (e.g., demographics and other baseline characteristics) are evenly balanced between treatment groups, and enable valid statistical comparisons between treatment groups. Subject treatment assignments will be unblinded after Phase 2 subjects have reached the Week 30 visit.

Phase 3 Segment

Subjects will be randomized (2 INO-4800:1 Placebo). Randomization will be stratified according to two factors, each with two levels: a) age-group age category (18-50 years vs. ≥51 years) on Day 0, and b) presence or absence on Day 0 of underlying medical conditions that increase risk of severe COVID-19 disease, per US CDC criteria.

The study is double-blinded. Randomization and blinding will avoid bias in the assignment of subjects to treatment, increase the likelihood that known and unknown subject attributes

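### The Phase 2 any-time adverse-event summary by arm pools blinded and open-label follow-up and should be split at the Week 30 unblinding

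*Protocol*

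**What the plan says.** All references are to protocol version 7.0 unless stated otherwise.

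- **Unblinding.** Section 5.2.1: "The Phase 2 segment of the trial will be unblinded following subjects reaching the Week 30 visit". Section 8.7 repeats it: "Subject treatment assignments will be unblinded after Phase 2 subjects have reached the Week 30 visit". The synopsis and Section 3.0 say the same.
- **Timing.** Week 30 in Phase 2 is the Day 210 clinic visit (Section 6.1.2.5: "Phase 2 segment: Day 210"). Section 6.1.2 adds: "All subjects will be followed until the Day 393 Visit".
- **Event collection.** Table 3, footnote h: "SAEs, MAAEs, and AESIs to be collected from time of consent to EOS". Other adverse events stop at Day 56.
- **Safety analysis.** Section 8.5.3.1 summarises events by arm in the Safety Population. The main summary covers 30 days after any dose and carries risk differences with Miettinen-Nurminen intervals. Then: "Separate summaries will be based on events occurring within 7 days of any dose and regardless of when they occurred". Frequencies by maximum severity and by strongest relationship to treatment are also planned. For Phase 2, all of this is repeated by prior receipt of a non-study COVID-19 vaccine.
- **Other vaccines.** Section 6.4.7 says that for Phase 2 subjects "the receipt of any non-study prophylactic COVID-19 vaccine (authorized under emergency use or licensed) is no longer restricted".
- **Status of Section 8.** Section 8.1 presents it as the formal statistical analysis plan, so the wording of 8.5.3.1 is the operative plan.

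**The concern.** Under version 6.0, Section 5.2.1 kept the sponsor, subjects and site staff (other than pharmacy) blinded for the whole trial, so an any-time comparison by arm was a blinded one. Version 7.0 brought in unblinding at Week 30 and carried the any-time sentence over unchanged. Section 8.5.3.1 was edited for non-study vaccines but not for unblinding.

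Three features make the late period sensitive to knowledge of assignment:

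- Section 7.8.2 defines a medically attended event by an unplanned contact with a health care provider. That depends on what the subject chooses to do.
- Section 7.10.4 leaves relatedness to the investigator, whose judgement is open-label after unblinding.
- Table 3 schedules no routine Phase 2 contact between Day 210 and Day 393. Late capture rests on spontaneous reports, any COVID-19 illness visits, and one final visit at which assignment is known.

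At stake is the long-term by-arm picture of SAEs and AESIs, which are Phase 2 secondary endpoints (Table 7), and of MAAEs. A reader of a single pooled table could not tell which counts arose under blinding.

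**Working it through.** The plan gives no figure of its own on this point, so the check is schedule arithmetic plus an illustration.

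**Schedule.** Week 30 is 30 × 7 = Day 210. Week 56 is 56 × 7 = Day 392, which agrees with Day 393 within the ±5-day window.

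**Which summaries contain open-label time?** Dose 2 is at Day 28 ± 3. The 30-day window therefore closes at the latest on about Day 28 + 3 + 30 = 61, and the 7-day window closes earlier. Both end roughly 150 days before Day 210. Only the any-time summary reaches past unblinding.

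**Open-label share of the any-time summary.**

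- Of all follow-up: (393 − 210) / 393 = 183 / 393 = 46.6%.
- With both visits at the edges of their windows: (388 − 215) / 388 = 44.6% to (398 − 205) / 398 = 48.5%.
- Of the time after Day 56, when only SAEs, AESIs and MAAEs are collected: 183 / (393 − 56) = 183 / 337 = 54.3%.

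These shares are maxima. The wording allows unblinding to wait until all Phase 2 subjects have reached Week 30, and early enrollees would then have less open-label time.

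**Illustration (assumed rates, not in the documents).** Let both arms have the same true constant hazard, with a proportion c having an event by Day 393, so hazard = −ln(1 − c) / 393. After Day 210, multiply placebo reporting by f. The apparent placebo proportion is p = 1 − exp[−hazard × (210 + f × 183)], and the spurious difference, active minus placebo, is c − p. Phase 2 has about 300 active and 100 placebo subjects (400 split 3:3:1:1), so SE = √[c(1 − c)/300 + p(1 − p)/100].

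| c | f | c − p (points) | Ratio c/p | SE (points) |
|---|---|---|---|---|
| 10% | 0.7 | +1.3 | 1.15 | 3.3 |
| 10% | 1.5 | −2.2 | 0.82 | 3.7 |
| 20% | 0.7 | +2.5 | 1.15 | 4.4 |
| 20% | 1.5 | −4.1 | 0.83 | 4.9 |
| 30% | 0.7 | +3.6 | 1.14 | 5.1 |
| 30% | 1.5 | −5.6 | 0.84 | 5.5 |

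The sign depends entirely on f, which nothing in the protocol fixes. Across these cases the distortion is at most about one standard error.

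**Does the planned vaccine split do the job?** No. A subject with no non-study vaccine still has blinded time before Day 210 and open-label time after it, and both sit in the same stratum. Receipt occurs after randomisation, and the plan does not say what it must be prior to, so the strata are neither randomised groups nor time periods.

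**The case against.** The case for leaving the plan alone is that the consequence is small. Much of it stands. The formal between-arm comparison belongs to the 30-day summary, which contains no open-label time; the any-time summary gives frequencies only. Phase 2 is estimation without hypotheses (Section 8.3). Dose selection used Week 6 and Week 8 data, and Phase 3 data are independent. SAEs are less open to reporting effects than MAAEs. This limits the point to one descriptive presentation, but that presentation is the only by-arm view of late events.

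A reader might also infer more than the documents support:

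- **That the pooling will make INO-4800 look safer**, because unblinded placebo recipients take another vaccine and its reactions count against placebo. Assuming uptake of 50–70% on placebo against 20–30% on INO-4800, and medically attended reactions in 5–10% of those vaccinated, gives 0.3 × 0.05 = 1.5 to 0.4 × 0.10 = 4 points. None of these rates is in the protocol, and reporting by subjects who know they had INO-4800 could move the result either way.
- **That non-study vaccination is a consequence of unblinding.** Section 6.4.7 attributes the lifted restriction to wider vaccine availability and completion of the dose-selection data. Receipt may precede Week 30. Unblinding may influence uptake, but that is a possibility and not a stated fact.
- **That Section 8.5.6 contradicts the unblinding** when it says "Thus, the trial will remain blinded to the Sponsor with respect to subject treatment assignment". That sentence closes the paragraph on who produces the group-level Week 6 and Week 8 summaries. It does not promise blinding to Week 56.

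**Conclusion.** The point holds as a limited defect in the presentation of late Phase 2 safety data. The any-time by-arm summary pools blinded time with up to 183 days of open-label time (47% of follow-up, 54% of the time after Day 56), and no planned stratification separates them. Late event rates, MAAEs above all, may be affected by knowledge of assignment. That is a risk and not a demonstrated bias, and its direction and size are unknown. The shares assume unblinding at each subject's Day 210 visit and follow-up to Day 393. The illustrative range of +3.6 to −5.6 points rests on assumed event and reporting rates. The conclusion does not extend to the 30-day or 7-day summaries, to dose selection or to Phase 3.

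**What to change.** In Section 8.5.3.1, for Phase 2, present the any-time by-arm summary of SAEs, AESIs and MAAEs, including the tabulation by relatedness, in two parts: events with onset before unblinding, as the controlled comparison, and events with onset after it, labelled open-label follow-up. Define the unblinding date used for the cut. Within each part, classify non-study COVID-19 vaccine receipt by its recorded date relative to event onset.

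Do not end follow-up at the first non-study vaccine. Section 8.5.3.1 reports crude percentages of subjects affected. If uptake differed by arm, stopping at vaccination would give the arms unequal and informative follow-up, and so a new bias.

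The cost is one extra date cut per table and a shorter controlled period for late events. No data are lost. Vaccine details and dates are already required on the CRF (Sections 4.3 and 6.4.6). The protocol does not say that an unblinding date is recorded, so its capture should be confirmed.
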